2 STUDY OBJECTIVES

2.1 Primary Objective

To evaluate the efficacy of four different dosages of deferiprone delayed release tablets in patients with Parkinson's disease.

The endpoints for the primary objective are provided in Section 9.1.1.

2.2 Secondary Objectives

- To evaluate the safety and tolerability of deferiprone delayed release tablets in patients with Parkinson's disease
- To evaluate the pharmacokinetics of deferiprone delayed release tablets in a subset of study participants
- To evaluate the relationship between the pharmacokinetics and pharmacodynamics of deferiprone delayed release tablets

The endpoints for the secondary objectives are provided in Section 9.1.2.

2.3 Exploratory Objectives

- To determine whether the efficacy responses to deferiprone differ depending on the genotype of certain enzymes that are implicated in Parkinson's disease
- To determine whether the efficacy responses to deferiprone are correlated with ceruloplasmin levels or ceruloplasmin ferroxidase activities

The endpoints for the exploratory objectives are provided in Section 9.1.3.

3 STUDY DESIGN

3.1 Description of Study Design

This is a multi-center, randomized, double-blind, placebo-controlled, dose-ranging study in 140 patients who have been diagnosed with typical Parkinson's disease within the last 3 years and are currently taking antiparkinsonian medication. Screening will be conducted within 30 days prior to the start of dosing. At baseline, eligible participants will be randomized to one of four dosage cohorts, and within each cohort will be further randomized in a 4:1 ratio to receive either active product or placebo. The assigned study product will be taken twice-daily (b.i.d.), at least 8 hours apart, for 9 months. Dosages are as follows:

- Cohort 1: 300 mg deferiprone delayed release tablets (n=28) or placebo (n=7)
- Cohort 2: 600 mg deferiprone delayed release tablets (n=28) or placebo (n=7)
- Cohort 3: 900 mg deferiprone delayed release tablets (n=28) or placebo (n=7)
- Cohort 4: 1200 mg deferiprone delayed release tablets (n=28) or placebo (n=7)

Patients will return to the site at Months 1, 2, 3, 4, 5, 6, and 9, and will receive a follow-up telephone call at Month 10. Safety will be assessed at each site visit and at the follow-up call; efficacy measures will be assessed at baseline and Months 3, 6, and 9; and sparse pharmacokinetics (PK) sampling will be done on all patients at baseline and Month 3. In addition, an optional subset of 16 patients will undergo extensive blood sampling for PK analysis at Month 1, and an optional subset of 18 patients will each provide one sample of cerebrospinal fluid (CSF) for drug level analysis at Month 3. (No selection will be done to enroll these subsets: all patients will be asked if they are willing to provide either or both of these types of samples, and they will be enrolled as they come until the total number of subjects is reached for each subset.) For safety reasons, all patients will have their absolute neutrophil count monitored weekly after the start of dosing. This procedure may be done either at either the study site or a local laboratory, or, with sponsor approval, at the patient's home by a visiting study nurse.

Any patient who withdraws before completing treatment will be requested to return within one month for an Early Termination visit, at which time the procedures normally scheduled for the Month 9 visit will be conducted.

3.2 Rationale for Study Design

The study is placebo-controlled since improvement, stabilization, or even a lesser worsening of motor symptoms in the active treatment groups compared to the placebo group would indicate efficacy.

The rationale for enrolling patients who are currently on antiparkinsonian medications is because the MDS-UPDRS scores of such patients are expected to be higher than those of patients who are treatment-naïve and recently diagnosed. Since the primary endpoint of the study is the change from baseline in MDS-UPDRS score, and the N is relatively small, the presence of higher scores at the start of the study should more easily permit the detection of a significant change in score between the deferiprone-treated and the placebo-treated groups. Furthermore, this population matches those used in investigator-led studies that showed promising results. ^{19,21}

The selection of study duration is based on findings in the literature. An investigator-driven pilot study found a significant difference between deferiprone and placebo after 6 months,

indicating that this duration might be sufficient to assess a symptomatic effect. However, in order to assess a delay in the progression of the disease, treatment of 9 months would be preferable. Indeed, in the only study to have successfully demonstrated such an effect in PD, treatment of 9 months was chosen as being a balance between being sufficiently long to observe the best global effect, but sufficiently brief to avoid the need for any change in current antiparkinsonian treatment. Hence, the duration of treatment in study LA48-0215 will be 9 months.

3.3 Rationale for Selection of Doses

The objective of this study is to determine what dose of deferiprone is likely to provide the most favorable benefit/risk ratio for the treatment of patients with PD: i.e., the balance between being high enough to have an effect but low enough to avoid clinically important toxicity. Data from two investigator-driven studies suggest that 15 mg/kg b.i.d. is the dose most likely to provide the greatest benefit vs. risk, but relatively few patients were enrolled in those studies. ^{19,21} In the case of thalassemia patients with systemic iron overload, dosages of Ferriprox are defined in terms of mg per kg of body weight; however, the span of weight in that patient population varies 10-fold, as both children and adults are being treated. In the case of PD, body weight is likely to vary less than 4-fold for the vast majority of patients, and according to key opinion leaders in the PD field, the average body weight in patients with PD is about 80 kg. Using 4 fixed doses of 300, 600, 900, and 1200 mg b.i.d. (i.e., for total daily dosages of 600, 1200, 1800, and 2400 mg) and an inclusion criterion of body weight between 60 and 100 kg, the following doses in terms of mg/kg/day should be obtained:

Actual Dose Received (mg/kg/day) When Prescribed Fixed Doses									
Body weight (kg)	300 mg b.i.d.	600 mg b.i.d.	900 mg b.i.d.	1200 mg b.i.d.					
60	10	20	30	40					
70	70 9		26	34					
80	8	15	23	30					
90	6	13	20	27					
100	6	12	18	24					

4 STUDY POPULATION

4.1 Number of Patients

A total of 140 patients will be randomized.

4.2 Inclusion Criteria

Individuals will be eligible to enroll in the study if they meet all the following criteria:

- 1. Male or female aged \geq 18 to <80 years
- 2. Body weight \geq 60 kg but \leq 100 kg
- 3. Diagnosis of Parkinson's disease according to UK Parkinson's Disease Society Brain Bank Clinical Diagnostic Criteria and based on the presence of at least two of the three cardinal features of the disease (rest tremor, bradykinesia, and rigidity). If rest tremor is not present, patient must have unilateral onset of symptoms.
- 4. Absolute neutrophil count $\ge 1.5 \times 10^9 / L$ ($\ge 1.0 \times 10^9 / L$ for Black population) at screening
- 5. On a stable dose for at least 3 months prior to the screening visit of any of the following treatments at an L-dopa equivalent daily dose of up to 600 mg:
 - o Dopaminergic agonist alone
 - L-dopa alone
 - o Combination therapy with dopaminergic agonist and L-dopa
 - o Rasagiline
- 6. At an early stage of the disease, without motor fluctuations and/or L-dopa—induced dyskinesia
- 7. A female patient must meet one of the following criteria:
 - If of childbearing potential, have a negative pregnancy test result at screening. In addition, she must:
 - Agree to use an effective method of contraception according to local requirements, during the study and for 30 days following the last dose of study medication, OR
 - b. Have undergone a tubal ligation (supporting evidence required), OR
 - c. Abstain from heterosexual intercourse, OR
 - d. Have a male sexual partner who has been sterilized (supporting evidence required)
 - Be of non-childbearing potential, defined as surgically sterile, having undergone complete hysterectomy or bilateral oophorectomy (supporting evidence required) or

being in a menopausal state (being 50 years of age or older and at least 1 year without menses)

- 8. Fertile heterosexual males must agree to use an effective method of contraception during the study and for 30 days following their last dose of study medication
- 9. All patients and/or their authorized legal representatives must provide signed and dated written informed consent prior to the first study intervention, and patients must be able to adhere to study restrictions, appointments, and evaluation schedules

4.3 Exclusion Criteria

Individuals will be excluded from enrollment if they meet any of the following criteria:

- 1. Diagnosis of Parkinson's disease more than 3 years prior to screening visit
- 2. Hoehn and Yahr stage ≥ 3
- 3. Atypical or secondary Parkinsonism without dopa-sensitivity (e.g., vascular parkinsonism, supranuclear palsy, multisystem atrophy)
- 4. Progressing Axis I psychiatric disorders (psychosis, hallucinations, compulsive disorders, substance addiction, bipolar disorder, severe depression, anxiety) as assessed in a semi-structured interview in accordance with the Diagnostic and Statistical Manual of Mental Disorders
- 5. Not stabilized in terms of the current antiparkinsonian therapeutic regimen: already requires dose adaptation and/or is likely to require any change in dopamine therapy over the duration of the trial
- 6. Current treatment with bromocriptine
- 7. Current treatment with any antiparkinsonian drug other than those listed in inclusion criterion #5
- 8. Current treatment with coenzyme Q10 or idebenone. (Patients who are on these medications but stop taking them at least 2 weeks prior to baseline may be enrolled.)
- 9. Current use of a Deep Brain Stimulation (DBS) system. (Patients who previously had a DBS system but have had it removed may be enrolled.)
- 10. History of malignancy, with the exception of cancers that have been in remission for ≥5 years at the time of screening
- 11. Evidence of abnormal liver or kidney function at screening (serum ALT level > 5 times upper limit of normal or creatinine levels >2 times upper limit of normal)
- 12. A serious, unstable illness, as judged by the investigator, during the past 3 months before screening visit, including but not limited to hepatic, renal, gastro-enterologic, respiratory, cardiovascular, endocrinologic, or immunologic disease

- 13. Disorders associated with neutropenia (ANC < 1.5×10^9 /L; < 1.0×10^9 /L in Black population) or thrombocytopenia (platelet count < 50×10^9 /L) in the 12 months preceding the initiation of the study medication. Exception: For patients whose neutropenia is attributed by the treating physician to episodes of infection or to drugs associated with a decline in the neutrophil count and in whom the ANC is back to a normal level at the screening visit.
- 14. Clinically significant abnormalities on 12-lead ECG, as judged by the investigator
- 15. Myocardial infarction, cardiac arrest, or cardiac failure within 1 year before screening visit
- 16. Bowel disease causing malabsorption
- 17. History of allergy or sensitivity to deferiprone or to other components of the formulation
- 18. Receipt of any investigational products within the past 30 days or 5 half-lives (whichever is longer) preceding the first dose of study medication
- 19. Participation in any investigational clinical study, other than observational, within the past 30 days; or plans to participate in such a study at any time from the day of screening until 30 days post-treatment in the current study
- 20. History of or current drug or alcohol use or dependence which in the opinion of the investigator would interfere with adherence to study requirements
- 21. Presence of any medical, psychological, or psychiatric condition which in the opinion of the investigator would cause participation in the study to be unwise
- 22. Pregnant, breastfeeding, or planning to become pregnant during the study period
- 23. Identified as an investigator or other site staff directly affiliated with this study, or an immediate family member (spouse, parent, child, or sibling, whether biological or legally adopted) of either of the above

4.4 Enrolment Violations

The criteria for enrolment must be followed explicitly. If there is inadvertent enrolment of a patient who does not meet the enrolment criteria, the investigator should consider withdrawing that individual from the study.

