1.4 Potential Risks and Benefits

Risks: The safety profile of deferiprone has been extensively characterized in patients with systemic iron overload. The most serious adverse event associated with its use in that population is severe neutropenia or agranulocytosis, defined as a confirmed absolute neutrophil count (ANC) less than 0.5×10^9 /L. In pooled clinical trials, agranulocytosis has been seen in about 2% of patients. The mechanism of deferiprone-associated agranulocytosis is unknown. Agranulocytosis usually resolves upon discontinuation of deferiprone, but there have been post-marketing reports of it leading to death. Accordingly, deferiprone recipients are required to undergo weekly hematology testing to ensure early detection of a drop in ANC. The most common non-serious adverse reactions reported during clinical trials have been chromaturia (due to iron excretion), nausea, vomiting, abdominal pain, increased alanine aminotransferase, arthralgia, and mild or moderate neutropenia (ANC less than 1.5×10^9 /L). The safety profile observed so far in patients with local iron overload has been found to be similar to that seen in the population with systemic iron overload, with respect to major risks. For detailed information on adverse events associated with deferiprone, see the Investigator's Brochure.

Benefits: The findings of preclinical and clinical research suggest that deferiprone has the potential to access pathologically relevant brain iron and to produce clinical benefit in patients with Parkinson's disease. The currently available medications for PD act only on symptoms, not on the underlying cause of the disorder. This treatment may possibly act to prevent the cell death that gives rise to those symptoms.

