4.5 Patient Withdrawal

Patients have the right to withdraw from the study at any time and for any reason without consequence to future care by the investigator or study site.

A patient may be withdrawn from the study at any time for any of the following reasons:

- Medical or safety reasons considered significant by the patient and/or the investigator
- Requirement for concomitant medication that might interfere with the evaluation of study treatment or may be contraindicated
- Occurrence of other illnesses that might affect the patient's further participation in the study or evaluation of study treatment
- A protocol deviation that might interfere with study assessments, as judged by the investigator
- Repetitive patient non-compliance with the protocol or with instructions of the investigator
- Any other situation where, in the opinion of the investigator, continuation of the study would not be in the best interest of the patient

A patient **must** be withdrawn from the study if any of the following conditions apply:

- Pregnant or planning to become pregnant during the study period (see Section 7.2.4, Procedures in Case of Pregnancy)
- Occurrence of severe neutropenia/agranulocytosis (see Section 7.2.1.8.1, Neutropenia)
- Occurrence of any adverse event characterized as life-threatening or disabling that is not associated with the patient's condition
- Receipt of a rescue medication (see Section 4.7 for definition)
- Termination of the study by the sponsor

Patients who decide to withdraw from the study should always be contacted, if possible, in order to ask about the reason for withdrawal, whether any adverse events (AEs) occurred, and use of concomitant medications. A withdrawn patient should return for an Early Termination Visit within one month of withdrawal. All study product and materials should be returned. If any AEs occurred, the investigator must attempt to follow up the outcome for 30 days post-termination.

If a patient withdraws or is withdrawn before completing the study, the date and reason for the withdrawal must be entered on the source document and on the appropriate page of the electronic case report form (eCRF), and all other appropriate eCRF pages must be completed.

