4.5.2 Replacement of Patients Who Withdraw

Patients who are withdrawn from the study will not be replaced.

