9 STATISTICAL ANALYSIS

9.1 Endpoints

9.1.1 Primary Endpoint

The primary endpoint is the change from baseline to Month 9 in the motor examination subscale (Part III) of the Movement Disorder Society-Unified Parkinson's Disease Rating Scale (MDS-UPDRS).

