9.3.2 Per Protocol Population

The PP population is defined as all randomized patients who complete the study, have no major protocol violations, and have an efficacy assessment at the end of the study. Prior to database lock, protocol violations will be reviewed for their seriousness, and patients with major violations will be excluded from the PP population. Only the primary efficacy endpoint will be analyzed for the PP population.

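### Section 4.4 prompts withdrawal from the study, not only from study drug, of randomised patients found ineligible, so Month 9 data can be lost avoidably; the likely effect is small

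*Protocol*

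**What the plan says.** Section 4.4 requires the entry criteria to be followed. It adds that, if an ineligible patient is enrolled by mistake, "the investigator should consider withdrawing that individual from the study". Enrolment here means randomisation: the synopsis counts 140 patients enrolled and section 4.1 counts 140 randomised.

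Section 4.5 separately lists as a ground for withdrawal "A protocol deviation that might interfere with study assessments, as judged by the investigator". It then describes what follows: "A withdrawn patient should return for an Early Termination Visit within one month of withdrawal". Section 3.1 describes that visit as the one "at which time the procedures normally scheduled for the Month 9 visit will be conducted". Section 4.5.2 states: "Patients who are withdrawn from the study will not be replaced".

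On the analysis side, the ITT set (9.3.1) is primary. It requires randomisation, one dose, a baseline and at least one post-baseline efficacy assessment. Eligibility is not a condition. For the PP set, section 9.3.2 provides for a review of violations before database lock, after which "patients with major violations will be excluded from the PP population".

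**The concern.** The primary endpoint (9.1.1) is the change in MDS-UPDRS Part III from baseline to Month 9. An investigator who acts on 4.4 ends the patient's efficacy follow-up before that point. The prompt has no test of materiality or safety, and it speaks of leaving the study, not of leaving treatment.

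The ITT analysis does not need these patients removed, and the PP definition already has its own step for excluding major violators. Section 4.4 therefore invites missing primary-endpoint data that neither analysis set requires. The decision is made case by case after randomisation, when the patient's course can be seen. The primary analysis in 9.4.1.3 assumes data missing at random, and discretionary removals need not satisfy that. A statistical analysis plan can model Month 9 scores that were never collected, but it cannot recover them.

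**Working it through.** **Tracing one patient through the text**

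1. The patient is randomised and later found ineligible; 4.4 prompts the investigator to consider withdrawal from the study.
2. If withdrawn, the patient is asked to attend one Early Termination visit within a month (3.1, 4.5). Month 9 procedures are done then. Unless withdrawal is late, that assessment precedes Month 9 and does not supply the endpoint at its time point.
3. No section schedules efficacy visits after withdrawal, and the place is not refilled (4.5.2).
4. The first scheduled post-baseline efficacy assessment is at Month 3 (Table 5.1). A patient withdrawn before then who also misses the Early Termination visit has no post-baseline efficacy assessment and leaves the ITT set (9.3.1).
5. The PP set requires completion of the study (9.3.2). A patient withdrawn under 4.4 for a minor violation is therefore outside PP whatever the review would have decided.

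**Allocation (5.2)**

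4 × (28 + 7) = 140 patients; 4 × 28 = 112 active; 4 × 7 = 28 pooled placebo. This reproduces the plan's figures. With placebo pooled (9.4.1) there are five groups of 28. Section 9.2 gives no power calculation, so there is none to check.

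**Size at an assumed violation rate**

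The protocol states no rate; 2-5% is an assumption.

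- Patients exposed: 140 × 0.02 = 2.8 and 140 × 0.05 = 7.0, so about 3 to 7.
- Average per group: 3/5 = 0.6 and 7/5 = 1.4. One patient is 1/28 = 3.6% of a group.
- Standard-error inflation if all are withdrawn and contribute nothing: √(28/27.4) = 1.011 and √(28/26.6) = 1.026, that is 1.1% to 2.6%.

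**A heavier assumed loss**

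Here *k* patients are lost from each of the two groups compared. Power is two-sided at 0.05 for an assumed standardised effect of 0.7, where 28 against 28 gives 74.5%. The last column is the shift in one group's mean, (*k*/28) × 5, if the lost patients would have differed from those retained by an assumed 5 points.

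| *k* lost per group | SE inflation √(28/(28−*k*)) | Power | Shift in one group's mean (points) |
|---|---|---|---|
| 1 | 1.8% | 73.0% | 0.18 |
| 2 | 3.8% | 71.4% | 0.36 |
| 3 | 5.8% | 69.7% | 0.54 |

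These figures treat a lost patient as contributing no data. Where Month 3 or Month 6 scores exist, the repeated-measures model uses them and the loss of information is smaller.

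**The case against.** The strongest reply is that 4.4 only asks the investigator to consider withdrawal. A patient with a trivial violation can be kept under the present wording, data already collected remain in the ITT analysis, a sensitivity analysis is planned, and reasons for withdrawal are recorded and summarised. All of this stands. It makes the loss possible, not certain, and limits its size. A reader might infer that the rule discards patients or their data; the text does not go that far.

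The PP set also cannot replace 4.4 entirely. Some entry criteria protect patients, and exclusion from an analysis set does nothing for a patient during the trial. That stands, but section 4.5 already allows withdrawal for safety or in the patient's interest. Which violations matter clinically is not judged here; section 3.3, for example, ties the weight limits to the intended exposure.

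Two further inferences are tempting and unsupported:

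- That withdrawals would be driven by unblinding through chromaturia. Section 1.4 lists it among the most common non-serious reactions, but its description centres on systemic iron overload. Section 1.1 says patients with Parkinson's disease lack generalised overload, and no rate is given for them. Any unblinding would affect every investigator judgement, not this one in particular.
- That a blinded PP review is already in place. Section 9.3.2 fixes its timing but does not say it is blinded. The blinded review in 9.4.1.3 concerns non-normality of the efficacy data.

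Finally, rewording 4.4 alone would leave similar discretion in the deviation bullet of 4.5. That is correct, and the fix has to cover both.

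**Conclusion.** The point holds as one about data retention. Section 4.4 can cause avoidable, discretionary loss of Month 9 primary-endpoint data, and it lets an investigator's decision during the trial settle PP membership before the planned review. The sections do not contradict one another; the weakness is that withdrawal from the study is the only course 4.4 names, and withdrawal ends efficacy follow-up.

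The effect is probably small. At the assumed 2-5% violation rate, with every exposed patient withdrawn and contributing nothing, standard errors rise by about 1-3%. A bias cannot be sized from the protocol; the shifts tabulated above rest on an assumed 5-point difference and an assumed loss. The case for change is that the loss is unnecessary and cheap to avoid, not that it threatens the trial.

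**What to change.** Amend section 4.4, and align the protocol-deviation bullet in 4.5 with it, to say that:

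- an enrolment violation is recorded as a protocol deviation;
- the patient is asked, with their agreement, to continue the scheduled efficacy visits through Month 9, whether or not study drug continues;
- PP status is decided at the 9.3.2 review before database lock, and that review is done blinded to treatment.

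Safety withdrawal under 4.5 and any decision on study drug stay with the investigator and are not changed.

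The cost is a short amendment to 4.4 and 4.5, a clause on blinding in 9.3.2, and a note in section 5.1 and Table 5.1 that these patients keep their efficacy visits. The visits are already in the schedule. The downside is a few extra visits for patients who would otherwise have left, and a few ineligible patients with complete data in the ITT set.
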